
### 1.6 Rationale of Daratumumab as a Consolidation Therapy before SCT and Maintenance Therapy in Post-SCT Settings for MRD Assessment

Our primary endpoint is to determine the percentage of patients with MRD negativity at Day 100 post SCT and at post-maintenance treatment for 1 year. Phase II multicenter single arm study was conducted in 10 IFM centers in France in 2009 to evaluate response after lenalidomide, bortezomib and dexamethasone (RVD) induction followed by SCT followed by 2 RVD consolidations and 1-year lenalidomide maintenance in 31 untreated transplant eligible MM patients. At the time of consolidation, 97% achieved PR, 87% at least VGPR, including 50% who achieved CR and among 26 evaluable patients, 15 (58%) were MRD negative. They evaluated MRD by bone marrow aspirate at post-induction/pre-ASCT, post-ASCT, post-consolidation and end of treatment regardless of

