## 2.0 Goals

### 2.1 Primary Objective:

To determine the percentage of patients achieving MRD negativity by MPF after autologous stem cell transplant (SCT) (at Day 100) using pre-SCT daratumumab consolidation.

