### 11.5 Response and Progression

Criteria for response and progression are listed in Table 11.5. Progressive disease for all patients as defined in Table 11.5.

Baseline values for disease assessment: All disease response measurements will be based on the values obtained at the time of diagnosis if there has been no relapse prior to transplant. If patients had a disease relapse prior to transplant, the baseline values will be those obtained at the time of relapse immediately prior to the transplant. If patient had treatment for the relapsed disease prior to transplant, the values will be from prior to this therapy, ie, the time of relapse.

Table 11.5

IMWG MRD NEGATIVITY CATEGORY	RESPONSE CRITERIA a
Flow MRD k	Absence of phenotypically aberrant clonal plasma cells by MPF on bone marrow aspirates using the EuroFlow standard operation procedure for MRD detection in multiple myeloma (or validated equivalent method) with a minimum sensitivity of 1 in $10^5$ nucleated cells or higher
Imaging + MRD-negative	MRD negative as defined by MPF or NGS PLUS Disappearance of every area of increased tracer uptake found at baseline or a preceding PET/CT or decrease to < mediastinal blood pool Standard uptake value or decrease to less than that of surrounding normal tissue
STANDARD IMWG RESPONSE CATEGORY	RESPONSE CRITERIA a
Stringent Complete Response (sCR) b	CR as defined plus Normal FLC ratio and • Absence of clonal PCs by immunohistochemistry or 2- to 4-color flow cytometry i
Complete Response (CR) b	• Negative immunofixation of serum and urine c and • Disappearance of any soft tissue plasmacytoma and • <5% PCs in Bone Marrow and • If the only measurable disease is FLC, a normal FLC ratio d
Very Good Partial Response (VGPR)	• Serum and urine M-protein detectable by immunofixation but not on electrophoresis c or • $\geq 90\%$ reduction in serum M-protein and urine M-protein <100 mg/24 h c • If the only measurable disease is FLC, a $>90\%$ reduction in the difference between involved and uninvolved FLC levels

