d In patients in whom the only measurable disease is by serum FLC levels: CR in such patients indicates a normal FLC ratio of 0.26-1.65 in addition to the CR criteria listed above.

e Bone marrow criteria for PD are only to be used in patients without measurable disease by M protein and by FLC;

f A "25% increase" refers to M protein, FLC and bone marrow results and does not refer to bone lesions, soft tissue plasmacytoma or hypercalcemia. The lowest value does not need to be a confirmed value. If the lowest serum M-protein is  $\geq 5$  g/dL, an increase in serum M-protein of  $\geq 1$  g/dL is sufficient to define disease progression.

g In the case where a value is felt to be a spurious result per physician discretion (for example, a possible lab error), that value will not be considered when determining the lowest value.

h Progressive disease should be confirmed on two consecutive evaluations, where the timing of confirmation is per the treating physician and can be done immediately within the same cycle or on the next cycle. However, treatment may be discontinued for progressive disease that is unconfirmed per physician discretion. In this case, an objective status of PD should be entered on the measurement form and progressive disease should be reported on the event monitoring form.

i Presence/absence of clonal cells is based upon the k/l ratio. An abnormal k/l ratio by immunohistochemistry requires a minimum of 100 plasma cells for analysis. An abnormal ratio reflecting presence of an abnormal clone is k/l of 4:1 or 1:2.

j Plasmacytoma measurements should be taken from the CT portion of the PET/CT, or MRI scans, or dedicated CT scans where applicable. For patients with only skin involvement, skin lesions should be measured with a ruler. Measurement of tumor size will be determined by the sum of the products of the maximal perpendicular diameters of measured lesions (SPD).

k Requires a complete response as defined in the table. MRD tests should be done as specified per the test schedule. MRD requires no known evidence of progressive or new bone lesions if radiographic studies were performed. However, radiographic studies are not required to satisfy these response requirements. **NOTE: An objective status of MRD negative should be reported on the treatment measurements form only when flow MRD by bone marrow is negative.**

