## 16.0 Statistical Considerations and Methodology

### 16.1 Overview

This is a phase II study of Daratumumab for transplant eligible multiple myeloma patients. This study is designed to assess the rate of minimal residual disease (MRD) negativity using a one stage phase II study design with an interim analysis in patients with transplant eligible multiple myeloma.

- 16.11 Primary Endpoint: The primary endpoint of this study is the rate of MRD negative response after ASCT. MRD negative response after ASCT is defined as achievement of MRD negative status in the bone marrow by flow cytometry (MPF) at the day 100 post ASCT visit. All patients meeting the eligibility criteria, who have signed a consent form and have begun treatment will be evaluable for response, unless they are determined to be a major violation.
- 16.12 Sample Size: The one stage study design with an interim analysis to be used is fully described below. A minimum of 20 and a maximum of 45 evaluable patients will be accrued total onto this phase II study unless undue toxicity is encountered. We anticipate accruing an additional 5 patients to account for ineligibility, cancellation, major treatment violation, or other reasons for a total of 50 patients overall.
- 16.13 Accrual Rate and Study Duration: The anticipated accrual rate is 2 evaluable multiple myeloma patients per month. Therefore, the accrual period for this phase II study is expected to be about 2 years. The maximum total study duration is expected to be approximately 5 years, or until the last patient accrued has been observed at least for 3 years after registration.

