### 16.3 Statistical Design:

#### 16.31 Decision Rule:

Previous studies of evaluation of minimal residual disease in multiple myeloma have been limited and have included small numbers of patients. In one previous study of lenalidomide, bortezomib and dexamethasone (RVD) induction followed by ASCT followed by 2 cycles of RVD consolidation and 1-year Lenalidomide maintenance in 31 untreated transplant eligible MM patients, an MRD negative response rate of 54% by flow cytometry was seen post ASCT in 26 evaluable patients tested. A MRD negative response rate of 65% by bone marrow flow cytometry would be of interest for this study.

The largest success proportion where the proposed treatment regimen would be considered ineffective in this population is 45%, and the smallest success proportion that would warrant subsequent studies with the proposed regimen in this patient population is 65%. The following one-stage design with an interim analysis is based on a two-stage Simon optimum design and requires 45 evaluable patients to test the null hypothesis that the true success proportion in this patient population is at most 45%.

- 16.311 Interim Analysis: Enter 20 evaluable patients into the study. If 9 or fewer successes are observed in the first 20 evaluable patients, we will consider this regimen ineffective in this patient population and terminate the

study. Otherwise, if the number of successes is at least 10, we will continue accrual.

16.312 Final Decision Rule: Enter an additional 25 evaluable patients into the study. If 24 or fewer successes are observed in the first 45 evaluable patients, we will consider this regimen ineffective in this patient population and terminate this study. Otherwise, if the number of successes is at least 25, this will be considered evidence of promising activity and the treatment may be recommended for further testing in subsequent studies in this population.

16.313 Over Accrual: If more than the target number of patients are accrued, the additional patients will not be used to evaluate the stopping rule or used in any decision making process.

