#### 16.41 Primary Outcome Analysis:

16.411 Definition: The primary endpoint of this trial is the rate of MRD negative response after ASCT. MRD negative response after ASCT is defined as achievement of MRD negative status in the bone marrow by flow cytometry (MPF) at the day 100 post ASCT visit. All patients meeting the eligibility criteria who have signed a consent form and have begun treatment will be evaluable for response, unless they are determined to be a major violation.

16.412 Estimation: The proportion of successes will be estimated by the number of successes divided by the total number of evaluable patients. Ninety-five percent confidence intervals for the true success proportion will be calculated according to the approach of Duffy and Santner.

16.413 Over Accrual: If more than the target number of patients are accrued, the additional patients will not be used to evaluate the stopping rule or used in any decision making processes; however, they will be included in final point estimates and confidence intervals

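### Section 16 counts a Day-100 success on marrow flow alone, but footnote k of Table 11.5 also requires a complete response; the two must be reconciled before successes are counted

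*Combined protocol and SAP*

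**What the plan says.** Section 16.1 gives the endpoint: "The primary endpoint of this study is the rate of MRD negative response after ASCT". Sections 16.11 and 16.411 then say that this response is "defined as achievement of MRD negative status in the bone marrow by flow cytometry (MPF) at the day 100 post ASCT visit". Objective 2.1 names the same assay and time point, and the two secondary MRD rates in Section 16.42 are also marrow MPF results. None of these places mentions CR or refers to Table 11.5.

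Section 16.31 states the 65% rate of interest as a marrow flow result. Beside it stands a benchmark: "an MRD negative response rate of 54% by flow cytometry was seen post ASCT in 26 evaluable patients tested".

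The working definition is the Flow MRD row of Table 11.5 in Section 11.5. It begins "Absence of phenotypically aberrant clonal plasma cells by MPF on" bone marrow aspirates and sets a minimum sensitivity of 1 in 10^5 cells. That row carries footnote k: "Requires a complete response as defined in the table". A note in the same footnote says that the MRD-negative objective status may be entered on the treatment measurements form only if the marrow flow result is negative.

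**The concern.** A patient who is flow-negative at Day 100 but has, say, a very good partial response is a success under Section 16.411 and not MRD negative under footnote k. The note in footnote k does not settle this. It makes a negative flow result necessary for the recorded status, not sufficient, so the CR condition remains.

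A site following footnote k could leave such a patient off the MRD-negative list while the statistician reads 16.411 as flow-only. Both decision rules (16.311 and 16.312) run on this count. The choice can only move patients from success to failure, so counting from the recorded status risks abandoning a regimen that meets the plan's own flow target. Left open, the choice could also be made after the data are seen.

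**Working it through.** **Inputs from the plan.** Section 16.31: null rate 45%, target rate 65%; stop if 9 or fewer successes in 20; declare the regimen ineffective if 24 or fewer in 45. Section 16.32: significance level 0.09, power 0.90.

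**Formulas.** With per-patient success probability p:
- P(stop at interim) = P(X1 ≤ 9), where X1 ~ Bin(20, p).
- P(declare promising) = sum over x = 10 to 20 of P(X1 = x) × P(X2 ≥ 25 − x), where X2 ~ Bin(25, p).

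**Reproducing Section 16.32.**

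| p | promising (plan) | promising (exact) | stop (plan) | stop (exact) |
|---|---|---|---|---|
| 0.45 | 0.09 | 0.0903 | 0.59 | 0.5914 |
| 0.50 | 0.25 | 0.2490 | 0.41 | 0.4119 |
| 0.55 | 0.49 | 0.4906 | 0.25 | 0.2493 |
| 0.60 | 0.74 | 0.7352 | 0.13 | 0.1275 |
| 0.65 | 0.90 | 0.9001 | 0.05 | 0.0532 |

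All ten entries agree. The design arithmetic is sound, and the only question is what is counted.

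**Applying footnote k.** Let d be the share of flow-negative patients not in CR at Day 100. The documents do not give d, so 0, 5, 10 and 20% are assumptions, applied independently to each flow-negative patient. The counted rate is the flow rate × (1 − d); for example, 0.65 × 0.90 = 0.585. The cut-offs are unchanged.

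| d (assumed) | counted rate at 65% flow | power | interim stop | counted rate at 45% flow | false-positive rate |
|---|---|---|---|---|---|
| 0% | 0.650 | 0.90 | 0.05 | 0.450 | 0.09 |
| 5% | 0.6175 | 0.80 | 0.10 | 0.4275 | 0.05 |
| 10% | 0.585 | 0.67 | 0.16 | 0.405 | 0.03 |
| 20% | 0.520 | 0.34 | 0.34 | 0.360 | 0.005 |

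Every CR-required success is also a flow-only success. The loss of power is therefore the probability that the two definitions give opposite conclusions on the same patients at a 65% flow rate: 0.9001 − 0.8044 = 0.10 at d = 5%, 0.9001 − 0.6675 = 0.23 at 10%, and 0.9001 − 0.3389 = 0.56 at 20%.

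**The case against.** The strongest reply is that Section 16 already answers the question. The objective, both endpoint definitions, the 65% target and both secondary MRD analyses are all worded as marrow flow results. Where Section 16 wants an IMWG category it names one: the overall response rate in 16.42 lists the qualifying response categories. If the specific text prevails over the general, the counts are flow-only and the figures in 16.32 stand. This carries weight, and Section 16 does favour the flow-only reading. It does not close the gap. Section 16.411 gives no assay sensitivity and no definition of negative, so the reader must go to Table 11.5, where the CR condition sits and where the recorded status is governed.

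Three stronger readings are tempting, and the documents do not support them.

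- **That discordance has been shown.** Section 1.6 reports, for the benchmark study around consolidation, "including 50% who achieved CR and among 26 evaluable patients, 15 (58%) were MRD negative". Setting 50% against 58% might suggest that some flow-negative patients were not in CR. But the sentence also gives 97% partial response and 87% at least very good partial response. No whole number out of 26 rounds to 97% or to 87%, and none out of 31 rounds to 50%. Between 24 and 31, only 30 fits all three (29/30, 26/30, 15/30). With 15 patients in CR and 15 MRD negative, the minimum discordance is zero. The figures are also not from Day 100.
- **That the benchmark is proven to be a flow-only count.** Section 1.6 says "They evaluated MRD by bone marrow aspirate at post-induction/pre-ASCT, post-ASCT, post-consolidation and end of treatment regardless of" response. That describes when marrow was tested, not how negativity was tallied. The scale of the design rests on the wording of the target in 16.31, which is enough.
- **That false positives are inflated.** The table above shows the opposite.

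**Conclusion.** The conflict holds. Section 16 defines and calibrates success on marrow flow alone, while the only working definition of flow MRD negativity, which also governs the recorded status, adds a CR. If the recorded status feeds the decision rules, power at a 65% flow rate is 0.80, 0.67 or 0.34 for assumed discordance of 5, 10 or 20%, against the stated 0.90, and interim stopping rises from 0.05 to as much as 0.34. The false-positive rate at a 45% flow rate falls from 0.09 to as low as 0.005.

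The size depends on two conditions that the documents leave open: that footnote k is applied to the counts, and that some flow-negative patients are not in CR at Day 100. If either fails, nothing changes. It would go too far to say that the trial is underpowered as designed. This is a reconciliation the sponsor should make, not a sample-size error.

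**What to change.** In 16.11 and 16.411, state that success is Day-100 marrow flow negativity at the Table 11.5 sensitivity, whatever the IMWG response category. In footnote k, add that its CR condition does not apply to the primary and secondary MRD endpoints. That is three sentences, with no new data and no change to the design figures.

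If the sponsor intends the CR-required version, which would be consistent with Section 11's adoption of the IMWG criteria, Section 16 should say so and restate 45%, 65% and the operating characteristics in 16.32 on that scale. That costs a fresh justification of the design.

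Either change should be made before the success counts are analysed. The interim count may already have taken place: activation was in April 2018, and at 2 patients a month 20 patients take about 10 months, plus about 8 months to the Day-100 visit, while the ninth amendment is still pending. The documents do not report its status. If it has been done, the plan should record which definition was used.

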## 11.6 Criteria for engraftment (for hematopoietic stem cell transplant studies only)

Engraftment is defined as:

- The first day of three consecutive days on which the absolute neutrophil count (ANC)  $>500/\text{mm}^3$  and
- The first of three consecutive days with an untransfused platelet count  $>20,000/\text{mm}^3$ .

## 12.0 Descriptive Factors

12.1 Depth of Response at registration: MRD positive sCR vs. MRD positive CR vs. VGPR vs PR vs SD

12.2 MM risk categories (As per Appendix IV): High vs. standard/intermediate vs. unknown.

12.3 Immediately prior treatment was maintenance: yes vs. no

12.4 Prior number of anti-myeloma regimens: 1 vs. >1 (NOTE: Any maintenance therapy given after an induction regimen is considered a part of that induction therapy and thus, 1 regimen)

12.5 Parameters followed for hematologic response (pick one) as per the time specified in section 3.18 : serum M-spike  $\geq 1$  g/dL and urine M-spike  $\geq 200$  mg/24 hours vs. serum M-spike  $\geq 1$  g/dL only vs. urine M-spike  $\geq 200$  mg/24 hours only vs. serum immunoglobulin free light chain  $\geq 10$  mg/dL vs. bone marrow cells  $\geq 30\%$ . Distinguish between SPEP measurements versus quantitative IgA measurements versus quantitative IgD measurements for serum M-spike.

## 13.0 Treatment/Follow-up Decision at Evaluation of Patient

13.1 Patients who are responding

Patients who are sCR, CR, VGPR, PR, MR, or SD (or usCR, uCR, uVGPR, uPR, uMR) will continue treatment per protocol. Treatment may continue until disease progression as long as the patient continues to respond and does not have any unacceptable toxicity.

13.3 Criteria for Initiation of Event Monitoring

Patients who go off protocol treatment for the following reasons will go to the event-monitoring phase per Section 4.2:

- Progressive multiple myeloma at any time on the clinical trial
- Patient requests to discontinue study treatment
- Patient develops an intercurrent illness that precludes further participation, or requires a prohibited concomitant treatment
- The Investigator withdraws the patient in the patient's best interests
- Administrative reasons (e.g., the patient is transferred to hospice care)
- An adverse event, which in the opinion of the Investigator, precludes further trial participation
- A dose omission of more than 28 days beyond the scheduled date of retreatment for daratumumab or lenalidomide

All attempts should be made to complete the End of Study procedures if a patient goes off treatment early.

